So it have been planned to conduct an experimental clinical trial using combination of ivermectin and doxycycline for treatment of COVID 19 along with the other standard care. It would be a randomized double blind placebo controlled Trial. The study would be conducted on 200 confirmed cases of Covid- 19. Another 200 patients will receive placebo.

The primary outcome would be the Days required for the Clinical improvement of the patients from the day of randomization.

Data will be analyzed using SPSS 20. Unpaired t-test would be used for testing quantitative data and for testing qualitative data two sample z- test would be used. For the comparison between two groups Hazard ratio, Kaplan-Meire curve, binary logistic regression would be used to see the outcome. Result of the study and statistical analysis will be presented by tables, figures, graphs, diagrams, charts and photographs. All these will have own legends (i.e. title) and will be serially numbered. Discussion will be done on the basis of result obtained from the study and comparing with similar studies done at home and abroad. Summarization will be drawn after discussion. Conclusion will be drawn depending upon the results and discussion.

PART - D

INTRODUCTION

On 31 December 2019, the World Health Organization (WHO) was formally notified about a cluster of cases of pneumonia in Wuhan City¹. On 7 January the causative virus was isolated and its genome sequence was shared on 12 January. The cause of the severe acute respiratory syndrome that became known as COVID-19 was a novel corona virus, SARS-CoV-2². The virus Spread quickly through out the universe in quick succession. The World Health Organization (WHO) on March 11, 2020, has declared the novel Corona virus (COVID-19) outbreak a global pandemic³.

Phylogenetic analysis suggests that SARS-CoV-2 originated in animals, probably bats, and was transmitted to other animals before crossing into humans at the Huanan wet market in Wuhan City⁴⁻⁵. It was the year 1918, when a new flu pandemic launched worldwide The pandemic infected 3% to 5% percent of the world's population including remote Pacific islands and the Arctic. The Life expectancy dropped by about 12 years⁶. The fatal casualties of the diseased had reached the number of the fifty million victims⁷.

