The number of days required for clinical improvement

1. Early Clinical improvement of the patients
How many days it requires to become the patient completely symptoms free
[Time Frame: 7 days]
2. Late clinical recovery
How many days the symptoms persist
[Time Frame: 12 days]

Secondary Outcome Measure:

1. Percentage of patients having clinical deterioration.
Patients deteriorating to next level of severity, like moderate, severe and death
[Time Frame: 1 month]
2. Persistently positive for RT-PCR.
Percentage of Covid-19 Patients repeatedly become positive for RT-PCR for Covid-19
[Time Frame: 14 days]

Data collection technique:

Data will be collected by assigned. trained data collectors (Physician).

Patient will be enrolled according to defined inclusion and exclusion criteria in the current research. Informed written consent will be obtained from the patient or their relatives. Each patient participating in the trial will be uniquely identified, and information such as his name, address is recorded in the trial 'subject number list'. Only the principle investigator will be aware about the allocation of the drugs. The patients

and the data collectors will be unaware about the group allocation of the drugs. The Data will be reviewed by the co-investigators. It will be managed by principle and co-principle investigators in designated computer.

Clinical assessment (fever, cough, Anorexia, Temperature, pulse, blood pressure, respiratory rate, oxygen saturation) will be done every day. Routine investigation (CBC, ESR, CRP, Creatinine, RBS, SGPT, chest x-ray, D- Dimer) will be done at admission and at day 3, 5, 7, 10 and 14 day. In case of the clinical deterioration it would done according to necessity. RT-PCR will be done at day-0, Day 5, day 7 and day 14.

Standard care: both the experimental and placebo will receive the available standard of care, like-

- Paracetamol, Antihistamine, Cough suppressant, Vitamins
- Oxygen therapy according to indication and need
- Low molecular weight heparin according to indication
- Appropriate other broad spectrum antibiotics
- Other drugs for associated co- morbid condition

Management of the adverse events:

Drugs adverse effect will be monitored by a defined committee. The patient experiencing adverse effect of the drugs will be discontinued from the study. It will be managed with priority to the highest possible level by the hospital authority as well as the investigators.

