These patients usually present with symptoms of an upper respiratory tract viral infection, including mild fever, cough (dry), sore throat, nasal congestion, malaise, headache, muscle pain, or malaise. Signs and symptoms of a more serious disease, such as dyspnea, are not present.

Moderate Pneumonia

Respiratory symptoms such as cough and shortness of breath (or tachypnea in children) are present without signs of severe pneumonia.

Severe Pneumonia

Fever is associated with severe dyspnea, respiratory distress, tachypnea (> 30 breaths/min), and hypoxia ($\text{SpO}_2 < 90\%$ on room air). However, the fever symptom must be interpreted carefully as even in severe forms of the disease, it can be moderate or even absent. Cyanosis can occur in children. In this definition, the diagnosis is clinical, and radiologic imaging is used for excluding complications.

Acute Respiratory Distress Syndrome (ARDS)

The diagnosis requires clinical and ventilatory criteria. This syndrome is suggestive of a serious new-onset respiratory failure or for worsening of an already identified respiratory picture. Different forms of ARDS are distinguished based on the degree of hypoxia. The reference parameter is the $\text{PaO}_2/\text{FiO}_2$:

- Mild ARDS: $200 \text{ mmHg} < \text{PaO}_2/\text{FiO}_2 \leq 300 \text{ mmHg}$. In not-ventilated patients or in those managed through non-invasive ventilation (NIV) by using positive end-expiratory pressure (PEEP) or a continuous positive airway pressure (CPAP) $\geq 5 \text{ cmH}_2\text{O}$.
- Moderate ARDS: $100 \text{ mmHg} < \text{PaO}_2/\text{FiO}_2 \leq 200 \text{ mmHg}$.
- Severe ARDS: $\text{PaO}_2/\text{FiO}_2 \leq 100 \text{ mmHg}$.

When PaO_2 is not available, a ratio $\text{SpO}_2/\text{FiO}_2 \leq 315$ is suggestive of ARDS.

Chest imaging utilized includes chest radiograph, CT scan, or lung ultrasound demonstrating bilateral opacities (lung infiltrates $> 50\%$), not fully explained by effusions, lobar, or lung collapse.

Clinical improvement Criteria

1. Body temperature remains normal for at least 3 days (ear temperature is lower than 37.5°C).

2. Respiratory symptoms are significantly improved.
3. Lung imaging shows obvious improvement in lesions.
4. There is no co-morbidities or complications which require hospitalization.
5. SpO₂, >93% without assisted oxygen inhalation.

8. FLOW CHART of Study workup:

Sl No	Activities						
		1 st	2 nd	3 rd	4 th	5 th , 6 th , 7 th	8 th

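### The primary event is defined in two incompatible ways, and the criteria list, read jointly, cannot be met by mild patients with a normal chest film

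*Protocol*

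**What the plan says.** **Primary Outcome Measure** (Protocol, Methodology). The outcome is headed "The number of days required for clinical improvement". It has two parts:
- Early improvement, over 7 days: "How many days it requires to become the patient completely symptoms free".
- Late recovery, over 12 days: "How many days the symptoms persist".

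**Operational definition, Clinical improvement Criteria.** Five numbered items are listed:
1. Ear temperature below 37.5 °C, held for three days or longer.
2. On symptoms: "Respiratory symptoms are significantly improved" (no threshold is given).
3. On imaging: "Lung imaging shows obvious improvement in lesions".
4. No comorbidity or complication that needs hospital care.
5. Oxygen saturation above 93% without supplementary oxygen.

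**Project summary, before the Introduction.** The outcome is "Days required for the Clinical improvement of the patients from the day of randomization".

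**Data collection technique.** Symptoms and vital signs are assessed daily. Routine investigations, which include the chest x-ray, "will be done at admission and at day 3, 5, 7, 10 and 14 day", with more as needed if the patient deteriorates.

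**Case record form.** Symptoms are daily yes/no rows to day 14. Temperature and oxygen saturation are also daily. Imaging has one findings field, with no day columns and no entry for improved or unchanged; a normal film is an allowed finding. Chest x-ray is not a row in the dated Investigations Profile.

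**The concern.** The outcome's name points to the list of clinical improvement criteria, while its description points to freedom from symptoms. These are different events, and nothing says which one governs. The Kaplan-Meier, log-rank and logistic analyses in the Data analysis section all need an event and a date for each patient, and here each can be derived in more than one documented way.

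What is at stake is the freedom to choose. The section on data collection says that the principal investigator knows the allocation and also takes part in managing the data. A choice between two written definitions, or a judgement about what counts as significant improvement, should not be left open in that setting.

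**Working it through.** **1. The plan's own figure.** The sample size section assumes response rates of 0.40 and 0.58. With its formula, N = ½ × [(1.96 + 0.845) / (arcsin√0.58 − arcsin√0.40)]² = ½ × (2.805 / 0.1810)² = 120.05, rounded up to 121. The stated 121 reproduces. The two rates are tied to neither definition and to no time point, so the calculation does not show which event was meant.

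**2. The two definitions side by side.**

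| Feature | Primary Outcome Measure | Clinical improvement Criteria |
|---|---|---|
| Symptoms | all gone | respiratory symptoms significantly better, no threshold |
| Temperature | not mentioned separately | normal for at least 3 days |
| Lung imaging | none | lesions clearly improved |
| Oxygen saturation | none | above 93% without oxygen |
| Need for hospital care | none | none remaining |
| Are the items joint? | single condition | not stated |

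Neither is uniformly stricter. The first is stricter on symptoms, the second on everything else. The yes/no symptom rows also cannot record a partial improvement.

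**3. Constructed patients.**
- Loss of smell persists to day 14, but all five criteria are met on day 7. This is an event on day 7 under the list and no event under the outcome section.
- A mild case with a normal film is symptom free on day 5. This is an event on day 5 under the outcome section. Under the list read jointly it is never an event, because there is no lesion to improve.

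The second patient is plausible. Mild cases are eligible, mild illness is defined as upper respiratory illness without dyspnoea, and the form allows a normal film.

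**4. Dating the imaging item.** Films fall at admission (day 0) and on days 3, 5, 7, 10 and 14, so the gaps are 3, 2, 2, 3 and 4 days. First improvement can be placed only within such a gap. There is no scheduled film on day 12, and the form has no dated place for a reading.

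**5. Dating the temperature item.** If temperature is normal on days 6, 7 and 8, the event is on day 6 (inside the 7-day frame) or day 8 (outside it). If it is normal on days 11, 12 and 13, the event is on day 11 (inside the 12-day frame) or day 13 (outside it).

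**6. Illustrations only, on assumptions the Protocol does not supply.** Power at 200 per arm is Φ(√(2 × 200) × |difference of arcsines| − 1.96).
- Suppose a share f of both arms cannot meet the imaging item and 0.40/0.58 hold in the rest. For f = 0 the rates are 0.40/0.58 and power is 95%. For f = 0.2 they are 0.32/0.464 and power is 84%. For f = 0.5 they are 0.20/0.29 and power is 56%.
- Suppose 0.40/0.58 are day-7 rates with exponential times. An event dated to its third day must begin by day 5. The rates are then 1 − 0.60^(5/7) = 0.306 and 1 − 0.42^(5/7) = 0.462, and power is 90%.

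**The case against.** The strongest reply is that a statistical analysis plan could choose one definition, that the criteria list does not say its items are joint, and that films taken on scheduled days carry dates even if the form does not. The second and third points stand as limits. The imaging problem for mild patients depends on the joint reading, which is the natural one for a numbered list but is not stated. Dating from source films is possible to within an interval. The first point does not remove the finding: these are two conflicting statements in the Protocol, not a detail left for later.

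A reader might infer more than the documents support:
- **That the 12-day measure in effect closes at day 10.** This holds only if imaging is the last item met. The item asks for improvement, not resolution, so a patient whose day 7 film already shows it can complete the other items on day 11 or 12. Even in that worst case, with exponential times and 58%/40% at day 7, recoveries fall from 77.4% and 58.3% (day 12) to 71.0% and 51.8% (day 10). The arm difference is 19.1 points against 19.2.
- **That the time origin is missing.** The project summary sets it at randomisation. The late measure only fails to repeat it.
- **That the two-day temperature ambiguity distorts the whole comparison.** It moves events equally in both arms and leaves their order for a log-rank test essentially unchanged. It matters at the cut-offs.
- **That the result is shown to change with the definition.** It can change; the Protocol gives no data to show that it does.

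**Conclusion.** The point holds: the primary event is not uniquely defined. The outcome section and the criteria list describe different events, with no link between them, no threshold for respiratory improvement, no statement on whether the five items are joint, no rule for normal baseline films and no event day for the temperature item.

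The size of the effect on the treatment comparison cannot be computed from the Protocol. It depends on the share of patients without lesions and on how often the two definitions disagree, and neither is given. The power figures above show what could be at stake under assumed shares; they are not estimates for this trial. That mild patients with normal films are unable to meet the list rests on reading it as joint.

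**What to change.** Reconcile Primary Outcome Measure with the Clinical improvement Criteria so that both state the same single event. Fix it before unblinding; since the principal investigator knows the allocation, that means before outcome data are examined. Count both the early and the late measure from randomisation, as the project summary does.

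A workable event is the first day on which all recorded symptoms are absent, temperature is below 37.5 °C and oxygen saturation is above 93% without oxygen, sustained for 3 consecutive days and dated to the first of them. Daily records run to day 14, so an event beginning on day 12 can still be confirmed (days 12, 13 and 14).

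Report lung imaging separately, in patients with lesions at baseline. If it stays in the primary event, state a rule for normal baseline films, say whether the items are joint, and add dated imaging fields with an improvement category.

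The cost is protocol wording plus small additions to the case record form. The form shown has an oxygen saturation row but none for oxygen use, so a daily oxygen-use row is needed. It also lacks malaise and muscle pain, which the definition of mild illness names; add both if symptom free is meant to cover them.

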If the patient progresses from mild to moderate or severe disease, the study will be continued and available management of the appropriate severity will be immediately started. The patient will be monitored closely.

Data analysis:

Data will be analyzed by computer with the help of SPSS (Statistical Package for Social Sciences) version 20. To compare mean of the two group chi square will be used. Comparing drug outcome in between two group survival analysis by Kaplan-Meier curve will be done for the duration of recovery. Odds ratio will be formulated from linear logistic regression for early and late clinical recovery. Hazard ratio will be formulated from the cox regression analysis for severity conversion and persistence of the positivity. Crude odds ratio will be adjusted in cox proportional hazard ratio model. Each Ivermectin-Doxycycline plus standard of care group will be compared with the placebo plus standard care group using the log-rank test, hazard ratio and 95% CI. Participants who were lost to follow up, died, discontinue drugs due to adverse effect will censored on the last study day. All P values will be two-sided and will be shown without

adjustment for multiple testing. All analyses will be performed according to the intention to treat principle.

Dropout management: Intention to treat measure will be taken

Observation and Results:

Result of the study and statistical analysis will be presented by tables, figures, graphs, diagrams, charts and photographs. All these would have own legends (i.e. title) and will be serially numbered.

Discussion:

Discussion will be done on the basis of result obtained from the study and comparing with similar studies done at home and abroad.

Summary:

Summarization will be drawn after discussion.

Conclusion:

Conclusion would be drawn depending upon the results and discussion

Conflict of interest:

Popular pharmaceutical will only provide drugs and the placebo.
None of the investigators will receive remuneration from the pharmaceutical company.
They will not get any access to data profile.

Operational definition:

(According to WHO guideline)

Confirmed Covid-19:

Cases with positive RT-PCR for Covid 19 irrespective of symptoms.

Uncomplicated (mild) Illness

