Clinical Feature

Trait			Follow-up Yes-1, No-2												
	On Enrollment		D 2	D3	D4	D-5	D-6	D-7	D-8	D-9	D-10	D-11	D-12	D-13	D-14
Fever	 Yes	 No													
Cough	 Yes	 No													
Running nose	 Yes	 No													
Sputum	 Yes	 No													
Respiratory distress	 Yes	 No													
Sore throat	 Yes	 No													
Hoarseness of voice	 Yes	 No													
Chest pain	 Yes	 No													
Diarrhoea	 Yes	 No													
Vomiting	 Yes	 No													
Anosmia	 Yes	 No													
Anorexia	 Yes	 No													
Headache	 Yes	 No													
Confusion	 Yes	 No													

Obsrvation

Trait		Follow-up Yes-1, No-2												
	On Enrollment	D 2	D3	D4	D-5	D-6	D-7	D-8	D-9	D- 10	D- 11	D- 12	D- 13	D- 14
Temperature														
Pulse rate														
BP														
Respiratory Rate														
Oxygen saturation														
Co- Morbidity	DM/HTN/ IHD/ HF/ CKD/CLD/Asthma/COPD/Malignancy/ CTD													

Investigations Profile

Trait	Value					
	Admission	D-3	D-5	D-7	D-10	D-14
Hb						
WBC						
Neutrophil						
Lymphocyte						
Platelet						
ESR						
CRP						
RBS						
Creatinine						
SGPT						
D-Dimer						
Na						
K						
ECG						
Covid-19 RT-PCR						

Radio-Imaging

Trait	Findings
Chest X-Ray CT Chest	Normal/ Consolidation (unilateral or bilateral) / Patchy opacity Consolidation/ Ground Glass Opacity/nodule/ multifocal

Principal Investigators:

Date:

Annexure-1

Popular Pharmaceuticals Ltd.

QUALITY ASSURANCE DEPARTMENT

Certificate of Analysis

Product Name: Placebo Tablet of Imec 6 Tablet

Batch No.: PB029

Mfg. Date: JUN 2020

Exp. Date: MAY 2022

Appearance: A pale yellow colored, round, standard bi-convex uncoated tablet with a break line on one side and other side plain

Composition:

SL. No.	MATERIAL NAME	QUANTITY PER TABLET	PERCENTAGE PER TABLET

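### Deterioration including death is a 1-month outcome, but the case record form stops at day 14, has no field for death, and no 1-month contact is described

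*Protocol*

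**What the plan says.** Under Secondary Outcome Measure, the protocol's first outcome is clinical deterioration, explained as "Patients deteriorating to next level of severity, like moderate, severe and death", with "Time Frame: 1 month". The Data analysis section plans a time-to-event analysis for it: "Hazard ratio will be formulated from the cox regression analysis for severity conversion and persistence of the positivity".

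Under Data collection technique, three kinds of assessment are described:

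- Clinical signs, with no end day: "respiratory rate, oxygen saturation) will be done every day".
- Routine investigations, which "will be done at admission and at day 3, 5, 7, 10 and 14 day".
- Virology: "RT-PCR will be done at day-0, Day 5, day 7 and day 14".

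For patients who get worse, the same section adds, about the investigations, "In case of the clinical deterioration it would done according to necessity". The section on adverse events says that patients who progress stay in the study under close monitoring, without giving a duration.

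Research instruments lists only the consent form and the CRF. The CRF is printed at the end of the protocol. Its symptom and observation grids, headed "Follow-up Yes-1, No-2", run from enrolment to D-14, and its investigations grid runs from admission to D-14.

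**The concern.** An outcome with a 1-month window needs each patient's status at 1 month, and a hazard ratio needs event dates and a known end of observation. The planned data appear to supply neither beyond day 14, and nowhere do they supply a record of death, the most serious component of the outcome.

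If the plan is followed as written, a figure labelled as 1-month deterioration would be built from data planned only to day 14. Later events would enter only if they happened to come to the staff's notice. The figure could then understate deterioration in both groups, and a reader could not tell how many patients were actually followed for the month.

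**Working it through.** There is no planned figure to reproduce. The check sets the outcome window against the schedule and the form.

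**1. Outcome windows against the last CRF column (D-14).**

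| Outcome | Time frame | Within D-14? |
|---|---|---|
| Primary 1, early improvement | 7 days | yes |
| Primary 2, late recovery | 12 days | yes |
| Secondary 1, deterioration including death | 1 month | no |
| Secondary 2, persistent RT-PCR positivity | 14 days | yes |

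Only the deterioration outcome, which is also the only one that includes death, runs past the form.

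**2. Length of the uncovered period.** The protocol gives no day count for a month, so 28 to 31 days is an assumption. Uncovered days = month length - 14; share = uncovered days / month length.

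- 28 days: 28 - 14 = 14; 14/28 = 50.0%
- 30 days: 30 - 14 = 16; 16/30 = 53.3%
- 31 days: 31 - 14 = 17; 17/31 = 54.8%

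**3. What the form can show about each component.**

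| Component | Enrolment to D-14 | Day 15 to 1 month |
|---|---|---|
| Moderate or severe disease | No severity grade, but largely derivable from cough, respiratory distress, respiratory rate and oxygen saturation, using the operational definitions | No column |
| Oxygen or ICU transfer | No field | No field |
| Death and its date | No field | No field |
| Discharge or final status | No field | No field |

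The derivation in the first row has one limit. The definition of severe pneumonia uses saturation below 90% on room air, and the form does not mark whether a reading was taken on room air or on oxygen.

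**4. Any other route to 1-month data.** The protocol describes no visit, call or vital-status check at or near 1 month. The CRF closes with the investigators' signature line and the placebo annexure follows, so nothing points to a further follow-up page. The form does collect a mobile number, but the protocol assigns it no use in follow-up.

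**The case against.** The strongest reply is that the text does not stop clinical assessment at day 14. Only the investigations and RT-PCR have a last day. Clinical signs are assessed daily with no stated end, tests are repeated as needed on deterioration, and progressing patients are monitored closely. The calendar also leaves room for longer follow-up, with primary completion on 25 August and study completion in September 2020. This stands as far as it goes: it would be wrong to say that the plan forbids or rules out data after day 14. But these provisions are undated, they react to deterioration already seen, and the one named form has nowhere to record what they find.

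Three stronger readings are tempting, and the documents do not support them.

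- A reader might infer that the outcome cannot be measured at all. For moderate and severe disease up to D-14 it largely can, with dates, from the daily entries.
- A reader might infer that patients are assumed event-free after day 14. The protocol does not say so. A Cox model censored at day 14 makes no such assumption; it simply estimates a 14-day hazard ratio. The difficulty attaches to the 1-month percentage and to the 1-month label. The Data analysis section does censor losses and deaths on a last study day that it does not define, so the intended end of observation remains open.
- A reader might take the 50-55% as the share of events missed. It is a share of calendar days. The protocol gives nothing on when deterioration occurs.

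The form's lack of an adverse-effect entry has no bearing on this outcome; monitoring of adverse effects is assigned to a committee.

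**Conclusion.** The point holds in a limited form. The protocol contradicts itself on one secondary outcome: the stated window is 1 month, while the dated tests and the only data form end at day 14, with no 1-month contact. What is missing is death with its date at any time, oxygen or ICU transfer and final status, and all status from day 15 to 1 month. That is 14 to 17 days, about 50-55% of the window, assuming a month of 28 to 31 days. The number of events this would miss cannot be estimated from the protocol.

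This is more than detail that an analysis plan could supply, because no analysis plan can recover data that the form does not collect. It does not touch the primary outcome, whose windows fit within the form. The correction should be made, and it is cheap.

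**What to change.** Choose one of two ways to align the window with the data:

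- **14-day outcome.** Restate the time frame as 14 days and limit the conclusion to 14 days. This costs a change of wording.
- **1-month outcome.** Add one status line to the CRF at a stated day count: alive or dead with date, and oxygen, ICU or hospital admission with date as the marker of worsening. Complete it by telephone, using the mobile number already collected. At 200 per group this is 2 x 200 = 400 calls. A call cannot measure respiratory rate or saturation, so the line should rely on dated care events and not on a severity grade.

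In both cases, add fields for death and its date and for severity class to the form through D-14, and mark each saturation reading as taken on room air or on oxygen. Define the last study day to match the chosen window, and reconcile the rule that censors deaths with an outcome that counts death as an event. These are changes to data collection and wording only.

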Covid-19 is an emergent pandemic, threatens the life of millions of the people throughout the globe. There is increasing effort of the scientist to unveil a remedy of covid-19. Still it is unsuccessful. At present there is no other alternative other than experimenting the existent drug against the virus. There are several trials going throughout the globe. Among them Ivermectin showed good efficacy in vitro trial. Some clinical trial also proved it beneficial. The Doxycycline also has some anti-viral role with its prominent anti-inflammatory role. Synergistic action of the two drugs might be proved some benefit in clinical trial. As both drugs are cheap and less toxic, if it does, it would be the blessing for the poor people of the globe.

4. METHODOLOGY:

Study type: Interventional Clinical trial

Estimated enrollment: 200 participants per group

For superior trial, the formula is:

$$N = \frac{1}{2} \times \left(\frac{Z_{\frac{\alpha}{2}} + Z_{\beta}}{\arcsin \sqrt{p} - \arcsin \sqrt{P_0}} \right)^2$$

N=size per group; p=the response rate of standard treatment group; p₀= the response rate of new drug treatment group; z_x= the standard normal deviate for a one or two sided x; d=

the real difference between two treatment effect; δ_0 = a clinically acceptable margin; S^2 = Pooled standard deviation of both comparison groups.

All parameters were assumed as follows: $p = 0.40$; $p_0 = 0.58$; $\alpha = 0.05$; $\beta = 0.20$; $\delta = 0.18$; $\delta_0 = 0.10$.

$$N_{\text{statistical superiority}} = \frac{1}{2} \times \left(\frac{1.96 + 0.845}{\arcsin \sqrt{0.40} - \arcsin \sqrt{0.58}} \right)^2 = 121$$

However, we are assuming that lost to follow up or refuse to include in trial will be 20%, that means 24. So at least 150 patients will be allocated randomly and power of this study will be 80%.

Allocation:

Randomized: Block randomization (Computer generated randomization code)

Intervention model: Parallel assignment

Intervention model description: Patient will be randomized 1:1 to placebo with standard care and combined doxycycline and ivermectin with standard care.

Blinding: Double blind (The participant and the clinicians/data collectors will be unaware of the treatment the participant receives)

Primary purpose: Treatment

Official title: A phase III trial to promote recovery from covid 19 with combined Doxycycline and Ivermectin along standard care.

Provider of placebo and active ingredients: Popular pharmaceutical limited

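### The one person who knows the allocation also manages the trial data, and no safeguard keeps data handling blind

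*Protocol*

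**What the plan says.** Under 4. Methodology, the trial is described as "Double blind (The participant and the clinicians/data collectors will be unaware of the treatment the participant receives". Randomisation is in computer-generated blocks; that section does not say who holds the code.

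Data collection technique assigns the roles:

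- Collection: "Data will be collected by assigned. trained data collectors (Physician".
- Knowledge of allocation: "Only the principle investigator will be aware about the allocation of the drugs". The next sentence keeps it from participants and from those who collect the data.
- Review: "The Data will be reviewed by the co-investigators".
- Management: "It will be managed by principle and co-principle investigators in designated computer".

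The primary outcome is the number of days to clinical improvement. The Clinical improvement Criteria, under Operational definition, combine numerical limits (temperature, oxygen saturation) with criteria that carry no threshold: a marked improvement in respiratory symptoms and an evident improvement on lung imaging. Data analysis censors participants who stop the drugs because of adverse effects.

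**The concern.** A matched placebo protects a trial only while those who can alter the data do not know the arm. Here a stated sentence gives the arm to one person, and another sentence makes that person a manager of the data. This is an arrangement the protocol fixes, not a detail it leaves to an analysis plan.

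Three kinds of decision made after data collection could be affected: corrections to recorded values, the day on which improvement is taken to have occurred, and the classification of a patient as discontinued for an adverse effect and so censored. Each feeds the time-to-improvement comparison. A lean in one direction, even an unintended one, would look like a treatment effect, and it could not be undone once the trial has been run.

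**Working it through.** **Step 1. Roles side by side (Protocol, Methodology and Data collection technique).**

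| Role | Who | Aware of arm? |
|---|---|---|
| Participant | – | No |
| Clinicians/data collectors | Trained physicians collect the data | No |
| Data review | Co-investigators | No, if the word only is literal |
| Data management | Principal and co-principal investigators | Principal investigator: yes |

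The exposure lies in the last row. The protocol describes no independent code holder, no restriction on what the principal investigator may do with the data, and no blinding until database lock.

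**Step 2. Can knowledge of the arm reach the primary outcome through data handling?**

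The Case Record Form as shown records symptoms as daily yes/no entries, together with vital signs and laboratory values. Imaging has a findings row without dates. The form has no field for clinical improvement or its date. A yes/no symptom entry cannot show whether respiratory symptoms have improved markedly, and an undated imaging entry cannot show when the lesions improved. If the Clinical improvement Criteria are applied, the day of improvement has to be settled from the collected data. The protocol does not say who settles it. Data management, which includes the unblinded person, is one place where that could happen.

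For censoring, Management of the adverse events says that a patient with an adverse effect of the drugs leaves the study. Calling an event a drug effect is a judgement. A committee monitors these events, but the investigators share in managing them, and the unblinded one is not excepted.

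**Step 3. Size.** The plan has no figure for bias to reproduce. The following only shows how sensitive the test is.

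Inputs from the protocol: 200 per group (Estimated enrollment), response 0.40 in the standard group (sample-size parameters, given without a time point), two-sided α = 0.05. Assumed, with no basis in the documents: a spurious shift b in one arm when there is no true effect.

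With p₁ = 0.40, p₂ = 0.40 + b and p̄ = (p₁ + p₂)/2:

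- SE₀ = √(2p̄(1 − p̄)/200)
- SE₁ = √((p₁(1 − p₁) + p₂(1 − p₂))/200)
- P(reject) = 1 − Φ((1.96·SE₀ − b)/SE₁) + Φ((−1.96·SE₀ − b)/SE₁)

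For b = 0.05:

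- p̄ = 0.425
- SE₀ = √(2 × 0.425 × 0.575/200) = 0.0494
- SE₁ = √((0.24 + 0.2475)/200) = 0.0494
- Upper tail: 1 − Φ(0.950) = 0.171
- Lower tail: Φ(−2.975) = 0.0015
- Total: 0.173

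| Assumed shift b | P(reject), no true effect |
|---|---|
| 0 | 5.0% |
| 2 points | 6.9% |
| 5 points | 17.3% |
| 10 points | 52.0% |

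This uses a comparison of proportions for simplicity. The protocol's main comparison is of time to recovery.

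**The case against.** The strongest defence is that the people who matter most are blinded. Double blind is defined as the participant and the clinicians/data collectors being unaware, and the data-collection text repeats this for patients and data collectors. Co-investigators review the data, management is shared with co-principal investigators, and a committee monitors adverse effects. The primary outcome is also described as days until the patient is free of symptoms, which can be read from the daily yes/no entries. All of this stands, and it narrows the point.

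It also rules out three stronger readings that a reader might infer:

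- **That the trial is not double blind.** That would follow only if the principal investigator treated patients or assessed outcomes. No text says so.
- **That the principal investigator signs the Case Record Form.** The form ends with a line headed, in the plural, for the principal investigators, and a date line. No duty to complete, sign or correct the form is described.
- **That allocation concealment is defeated.** Someone who knows past assignments in a block can sometimes predict the next, but no text gives the principal investigator a part in enrolment. None excludes it either, so this is a conditional risk.

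The defence does not remove the remaining problem. Blinded collection and review do not blind a co-manager of the dataset, and the protocol does not say whether symptom freedom or the Clinical improvement Criteria determine the endpoint. The blinding and independence of the committee are not stated.

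**Conclusion.** The point holds in a limited form. The principal investigator is the only person who knows the allocation and is also a manager of the data, with no stated safeguard. Blinding of participants and data collectors is intact as the protocol defines it; blinding of data handling is not protected. The consequence is greatest if the unquantified improvement criteria are used, because dating improvement then needs judgement.

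The size of any bias cannot be derived from the documents. The rejection rates of about 7%, 17% and 52% rest on assumed shifts of 2, 5 and 10 points. They show what such shifts would do, not that any would occur. The case for changing the text is that it closes a route for bias at little cost.

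**What to change.** Replace the sentence "Only the principle investigator will be aware about the allocation of the drugs" with a statement to this effect:

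- The randomisation code is held by an existing party independent of patient care, enrolment, outcome assessment and data management.
- Study drug and placebo are supplied in sequentially numbered packs of identical appearance.
- A sealed envelope for each patient allows that patient's code alone to be broken in an emergency.
- All investigators, including the principal investigator, remain blinded until database lock.

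Whoever packs or dispenses the study drug could hold the code, provided that party has no access to trial data. If the supplier is chosen, Conflict of interest needs a small edit. It limits the company to providing drugs and placebo, and its sentence "They will not get any access to data profile" follows one about the investigators, so it is unclear to whom it applies.

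The cost is minor pack-numbering and envelope work. The downside is that an emergency unblinding requires an envelope to be opened.
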